Study surveys were developed by the study team and based on extant literature. Surveys will be delivered via REDCap and completed on a

smart phone, desktop, or tablet computer. Surveys and their domains are listed below.

- Adolescents:
 - Baseline Survey (intervention, control arms): unique code questions,³⁹ demographics, ARA victimization and perpetration,^{35,40,41} recognition of abusive behaviors,^{35,41} self-efficacy,⁴² consequences of ARA, ARA resource knowledge/use,³⁵ readiness to engage in healthy relationship behaviors
 - Exit Survey (intervention arm only): fidelity, acceptability, self-efficacy,³⁵ use of POC resources, ARA disclosure
 - Follow-up Survey (intervention, control arms): unique code questions,³⁹ ARA victimization and perpetration,^{35,40,41} recognition of abusive behaviors,^{35,41} self-efficacy,³⁵ consequences of ARA, ARA resource knowledge/use

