25.0 Data Collection*

Sources of data include adolescent participants (surveys, audio recordings of ED-HEART delivery), the medical records of adolescent participants (chart review by study team), the Cerner ED tracking board, and Health Educator field notes. See Section 9 (Surveys and Psychometric Testing) for a detailed description of survey data. **Sensitive Data:** Study data includes report of ARA and receipt of POC RSH resources accessed during the ED visit.

Identifiable Data: PHI sufficient to enable delivery of the study follow-up survey and to enable monitoring of intervention fidelity (i.e., audio recording of ED-HEART delivery) will be recorded. This information will not be retained as a part of permanent study data.

| | | |
|------------------|----------------------------------------|----------------------------------------------|
| 1. Name/Initials |  Accessed only |  Recorded |
|------------------|----------------------------------------|----------------------------------------------|

| | | |
|-------------------------------------------------------------------------------------------------------------------------------------------------------------------------------|----------------------------------------|----------------------------------------------|
| 2. All elements of date (except year) directly related to an individual (e.g., date of birth, admission date, discharge date, date of death) |  Accessed only |  Recorded |
| 3. Medical record number |  Accessed only |  Recorded |
| 4. Account number |  Accessed only |  Recorded |
| 5. Health plan identification number |  Accessed only |  Recorded |
| 6. Social Security Number |  Accessed only |  Recorded |
| 7. Device identifiers and serial number |  Accessed only |  Recorded |
| 8. Certificate/License number |  Accessed only |  Recorded |
| 9. Telephone number |  Accessed only |  Recorded |
| 10. Fax number |  Accessed only |  Recorded |

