(yes or no) as a covariate, and study arm as focal predictor. This approach should have higher statistical power than the Fisher's Exact Test used in the power analysis, making our sample size somewhat conservative. We will analyze secondary outcomes (ARA perpetration, ARA victimization, recognition of abusive behaviors, knowledge of ARA resources, self-efficacy to use harm reduction strategies, use of harm reduction strategies and resources) similarly. Factors potentially affecting intervention efficacy (e.g., sex, gender, race/ethnicity, recognition of behaviors as abusive, intention to engage in healthy relationship behaviors, adolescent change talk, MI fidelity [MI-consistent/-inconsistent behaviors], intervention intensity [number of intervention topics discussed]) will be considered as additional model predictors. We will summarize demographics and report baseline prevalence of any ARA and individual types of ARA. We will check for differences in demographics and baseline variables between the two arms, as well as for demographic differences between participants and refusals.

2.3 A sample size of 69 per arm provides 80.4% power to detect a between-arm difference, assuming control and intervention arm TVD rates of 0.55 and 0.30, respectively, at 3 months at follow-up (two-sided Fisher's Exact Test at alpha=0.05). We set a final sample as n=174 participants (n=87 each arm) to account for an estimated 20% loss to follow up, based on our previous work.

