### 4.2 Scope of the analyses

The analysis will assess feasibility of the ED-HEART intervention through the eight Bowen model feasibility constructs. Additionally, the analysis will examine theory of planned constructs (attitudes, beliefs, perceived behavioral control, intention) to facilitate exploratory analysis of factors that may contribute to differential outcomes. Comparisons will be made between the standard of care study arm (control study arm) and the ED-HEART study arm with respect to demographics and survey questions.

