#### Secondary aims:

Secondary aims that will be explored include: 1) examine the Theory of Planned Behavior constructs that may impact the efficacy of ED-HEART, and 2) conduct exploratory analysis of factors that may additionally impact efficacy and/or implementation of ED-HEART.

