## 8 General Analysis Considerations

### 8.1 Planned Analyses

Descriptive summaries will be made for the Bowen model's eight constructs regarding feasibility (primary outcome). Specifically, the measures defined in the table below will be summarized.

Assessment of Bowen Feasibility Constructs		
Construct	Definition	Assessment measures
Acceptability	To what extent is ED-HEART suitable?	Adolescent surveys, Health Educator field notes
Demand	To what extent is ED-HEART likely to be used?	Proportion of screened adolescents eligible; proportion of eligible adolescents enrolled; Health Educator field notes
Implementation	To what extent can ED-HEART be delivered as planned?	Fidelity assessment per adolescent survey, Health Educator field notes, audio recordings of intervention delivery
Practicality	What factors make delivery challenging or facilitate delivery?	Health Educator field notes
Adaptation	To what extent does ED-HEART perform in a new system?	Comparison with published outcomes in original setting 
Integration	To what extent can ED-HEART be integrated within existing system?	Health Educator field notes
Expansion	To what extent can the existing system be expanded to provide ED-HEART?	Health Educator field notes
Limited efficacy	Are ED-HEART outcomes promising?	Primary outcome: any ARA at 3-month follow up  , per adolescent survey

Acceptability ratings will be collapsed to dichotomous variables. ED-HEART will be deemed acceptable if the test of the proportion of very/fairly satisfactory ratings for adolescents, the health educator, and ED staff being at least 85%. We will compare ED length of stay between the two arms and calculate the mean/median number of interruptions per participant, with a list of reasons for interruption. For limited efficacy assessment, our primary outcome is any ARA as individual types of abuse rarely occur in isolation and HEART is designed to address ARA broadly. We will compare odds of reporting ARA at follow-up for the two arms by fitting a logistic regression model with any ARA victimization at follow-up (yes or no) as the dependent variable, baseline ARA (yes or no) as a covariate, and study arm as focal predictor. This approach should have higher statistical power than the Fisher's Exact Test used in the power analysis, making our sample size somewhat conservative.

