We will analyze secondary outcomes (ARA victimization, recognition of abusive behaviors, knowledge of ARA resources, self-efficacy to use harm reduction strategies, use of harm

reduction strategies and resources) similarly. Factors potentially affecting intervention efficacy (e.g., sex, gender, race/ethnicity, recognition of behaviors as abusive, intention to engage in healthy relationship behaviors, adolescent change talk, MI fidelity [MI-consistent/-inconsistent behaviors], intervention intensity [number of intervention topics discussed]) will be considered as additional model predictors. We will summarize demographics and report baseline prevalence of any ARA and individual types of ARA. We will check for differences in demographics and baseline variables between the two arms, as well as for demographic differences between participants and refusals.

Additional analysis will include looking into the mismatching of the special code, assessing data in aggregate at each timepoint (e.g., baseline and 12-week follow-up), examining findings in those that have both baseline and follow-up linked surveys completed for how responses may have changed, and investigate those that did not follow-up.

Analysis will begin after the final enrolled patient is 13 weeks out from enrollment.

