## **8.3 Missing Data**

Missing data will be excluded case-wise by analysis and noted for variables missing large portions. It is anticipated that not all follow-up surveys will be able to be linked to the baseline surveys due to data entry errors. No imputation will be used.

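### The search for factors affecting ED-HEART efficacy adds them as predictors, which does not show differential efficacy; three of them are measured during the ED-HEART session

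*SAP*

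**What the plan says.** SAP 5.2 gives as a secondary aim to "conduct exploratory analysis of factors that may additionally impact efficacy and/or implementation of ED-HEART". SAP 4.2 describes the purpose as "exploratory analysis of factors that may contribute to differential outcomes".

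The limited-efficacy model in SAP 8.1 is a logistic regression of ARA at follow-up with "baseline ARA (yes or no) as a covariate, and study arm as focal predictor". SAP 8.1 then lists factors that might affect efficacy, such as sex, gender, race/ethnicity, recognition of abuse and intention, and ends the list with "adolescent change talk, MI fidelity [MI-consistent/-inconsistent behaviors], intervention intensity [number of intervention topics discussed]) will be considered as additional model predictors". Protocol 27.0 says the same: "intervention intensity [number of intervention topics discussed]) will be considered as additional model predictors". SAP 8.2 adds further factors without a method and allows for possible subgroups by ARA status. SAP 10 plans Tables 2 and 3, which compare ARA bivariately across all variables, one table per arm.

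The sources described for session content belong to the ED-HEART arm. Protocol 25.0 lists "audio recordings of ED-HEART delivery", and Protocol 9.0 describes the "Exit Survey (intervention arm only): fidelity, acceptability". SAP 6.1 likewise gives the exit survey only to the ED-HEART arm. On missing values, SAP 8.3 says: "Missing data will be excluded case-wise by analysis", with no imputation.

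**The concern.** Efficacy is a contrast between arms. A factor affects efficacy only if that contrast differs across its levels, and an added main effect cannot show this. Read as written, the plan could report a factor that merely predicts ARA as one that alters the benefit of ED-HEART, and could miss one that does alter it.

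The three session measures raise a separate problem. Change talk, MI fidelity and number of topics arise after randomization, during an encounter that controls do not have. If controls have no values, these measures cannot sit in a model that also estimates the arm effect. If controls were given a value such as zero topics, the arm coefficient would change meaning.

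**Working it through.** **1. The plan's own figure.** SAP 7 assumes 69 per arm, rates of 0.55 and 0.30, and a two-sided Fisher's exact test at 0.05. Exact enumeration gives power 0.8040, matching 80.4%. For 20% loss, 69/(1 − 0.20) = 86.25, so 87 per arm and 174 in total. Nothing below changes this.

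**2. What each term estimates.**
- As written: logit P(ARA) = β0 + β1·arm + β2·baseline ARA + γ·factor. The arm log odds ratio (OR) is β1 at every level of the factor.
- With a product term δ·arm×factor, the arm log OR is β1 + δ·factor, and exp(δ) is the ratio of arm ORs. Only δ bears on differential efficacy.

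Example with an assumed 50:50 factor: control rates 0.475 and 0.625 (mean 0.55), ED-HEART rates 0.375 and 0.225 (mean 0.30).
- Arm OR at level 0: (0.375/0.625)/(0.475/0.525) = 0.663.
- Arm OR at level 1: (0.225/0.775)/(0.625/0.375) = 0.174.
- Ratio: 0.663/0.174 = 3.8.
- Average ARA over both arms: (0.475 + 0.375)/2 = 0.425 at level 0 and (0.625 + 0.225)/2 = 0.425 at level 1.

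The arm effect differs almost fourfold, yet the factor has no average association for a main effect to find.

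**3. Simulated trials.** Wald tests at two-sided 5%, 69 per arm, rates 0.55/0.30. Assumed: baseline ARA 55%, baseline OR 2–4, binary factor with prevalence 30–50%.

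| Assumed truth | Added predictor significant | Arm × factor term significant |
|---|---|---|
| Prognostic only: OR 3 in both arms | 76–84% | 4–5% |
| Modifier: ratio of arm ORs 3, no average association | 5–6% | 28–32% |
| Modifier: ratio 3, factor acts in one arm only | 25–35% | 24–32% |

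In the second row the model without a product term shows a single arm OR of 0.30–0.33. The product term recovers a ratio of about 3.1.

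A second set of 2,000 trials per scenario, without baseline ARA, agrees. A prognostic factor with log OR 1.2 was significant as a main effect in 92% and as a product term in 4.1%. The example in step 2 gave 5.1% and 46%.

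**4. Tables 2 and 3.** With the same factor OR (2 or 3) in both arms and no modification, a chi-square test was significant in exactly one arm in 33–51% of simulated trials. Reading the two tables side by side by significance would therefore often suggest a difference that is not there.

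**5. Session measures.**
- *Controls missing.* Case-wise exclusion leaves no controls. With columns for intercept, arm, baseline ARA and the session measure, the design has rank 3 of 4, so the arm effect is not estimable.
- *Topic count coded 0 in controls* (a coding the documents do not state). With topics assumed uniform on 1–4 or 2–6, the arm standard error (SE) rises from 0.37–0.39 to 0.72–0.89. With topics 1–6, effect proportional to topics and no baseline covariate, the median arm log OR moves from −1.02 to 0.02 and the rejection rate from 83% to 4%. The coefficient has become an effect extrapolated to zero topics. This case does not cover change talk or MI fidelity.

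**6. Precision of the alternative.**
- Formula: SE = √Σ 1/[n·p(1 − p)].
- Arm effect: √(1/(69 × 0.2475) + 1/(69 × 0.21)) = 0.357.
- Arm × factor, 50:50 factor (34.5 per cell): √(2/(34.5 × 0.2475) + 2/(34.5 × 0.21)) = 0.714, twice as large. The 95% factor is exp(1.96 × 0.714) ≈ 4.1; at 30% prevalence the SE is 0.779 and the factor about 4.6.
- With baseline ARA in the model, simulation gives ×/÷ 4.3–5.5, or 5.2–6.6 if only 55 per arm can be linked (an assumed 80% of 69).
- Within ED-HEART there are about 0.30 × 69 ≈ 21 events, and the OR per topic has 95% limits of ×/÷ 1.5–1.7.

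**The case against.** The wording is permissive. A product term is also a model predictor, nothing excludes one, and differential outcomes in SAP 4.2 could mean outcomes that vary between adolescents rather than a varying treatment effect. That is fair, but SAP 5.2 and 8.1 both speak of efficacy, and the only form named is an added predictor.

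The missed-modifier figure is an extreme case. When the factor acts in one arm only, the added predictor is significant about as often as the product term (25–35% against 24–32%). This stands as a limit on the missed-modifier argument. It does not rescue the method, because a significant added predictor still cannot tell a modifier from a prognostic factor.

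Table 3 could already hold a within-arm listing of the session measures, which is part of the remedy. It is bivariate, however, without baseline ARA, and nothing keeps these measures out of the two-arm model. The failure with missing controls would be visible to the analyst, and zero coding is hypothetical. Both points stand.

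That controls lack change-talk data is an inference. Protocol 25.0 also lists Health Educator field notes without restricting them to one arm. The objection to main effects does not depend on this.

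Finally, no document says that significance alone will decide which factors are reported, and interactions here are imprecise. This is why the remedy is limited to estimates with intervals.

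**Conclusion.** The concern holds, as a minor point confined to the exploratory aim. Added main effects do not measure differential efficacy: under the assumptions in step 3, a prognostic-only factor would be flagged in 76–84% of trials, and a modifier with no average association in only 5–6%. The latter is a deliberately chosen extreme. The three session measures do not belong in a model that estimates the arm effect; that conclusion rests on the inference that controls have no values, which is strongest for MI fidelity and topic count. The primary model of arm plus baseline ARA and the sample size are unaffected. Factor prevalence, factor and baseline odds ratios, baseline ARA of 55% and topic ranges are assumptions, not figures from the plan.

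**What to change.** State two things in SAP 8.1 and align Protocol 27.0:

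1. For baseline factors measured in both arms, effect modification is examined by adding an arm × factor term to the primary model. Arm ORs are reported by factor level with 95% confidence intervals and no significance claims.
2. Change talk, MI fidelity and number of topics are not entered in any model used to estimate the arm effect. They are analysed within the ED-HEART arm, with baseline ARA as covariate, as descriptive non-randomized associations, where recordings can be linked to follow-up surveys.

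The point-of-care resources factor in SAP 8.2 should be assigned to one of these groups. Its use is captured in the exit survey, which controls do not complete.

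The cost is two sentences and a few exploratory fits, with no change to sample size, data collection or the primary analysis. The downside is imprecision: interaction intervals of about ×/÷ 4.3–5.5, wider if linkage is incomplete, so the results can only be descriptive. The second part also depends on joining recording-derived measures to surveys. Protocol 28.0 keeps survey data unlinkable to identity and no such join is described, so this must be confirmed first.

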## **8.2 Covariates and Subgroups**

Factors potentially effecting efficacy will be investigated. These include but aren't limited to age, race/ethnicity, gender, sexual orientation, insurance status, chief complaint in the ED, POC resources, and relationship status. Depending on results from the proposed analysis and provided the available sample size, subgroups by ARA status may be explored.

## **8.3 Missing Data**

Missing data will be excluded case-wise by analysis and noted for variables missing large portions. It is anticipated that not all follow-up surveys will be able to be linked to the baseline surveys due to data entry errors. No imputation will be used.

## **8.4 Interim Analysis and Data Monitoring (as applicable)**

No interim analysis is planned. No data monitoring committee will be needed due to the minimal risk exemption. Data will be collected via REDCap and stored per CMH's record retention policy. The final dataset will be locked after the final enrolled patient was 13 weeks out from enrollment.

## **8.5 Adjusting for Bias**

We will examine enrolment bias by comparing demographic (age and gender) in those that enrolled and those that refused. Allocation to study group will only be performed after consent/assent to participate has been. No personal identifiers are entered into the system due to coding system. We will utilize the 6-week check-in to remind participants of the 12-week survey follow-up as outlined in study procedures section to optimize the final outcome data.

## **8.6 Adverse Events**

This study has been designated as “minimum risk.” No adverse events, serious adverse events, and/or death are anticipated. PI and study team will meet weekly during enrollment and the 3-month follow-up period to identify and discuss adverse events and unanticipated problems. Provided any adverse events occur, a safety table will be included in the supplement.

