11.0 Follow-up

- Participants will complete a 6-week check-in to confirm and update contact information. This will be done via email, text, that has the weblink to a REDCap survey that asks if current contact information is current and offers opportunity to update contact information if needed. We will send up to 2 emails and/or 2 text reminders for the 6-week check in. If by week 7 the participant has not completed the follow-up survey, a study team member will call them using the phone number(s) provided to remind them about the survey (maximum number of phone calls = 3). If needed at the time of the call, the follow-up survey weblink will be sent via email and/or text.
- Option to notify participants of 6-week check in and 12-week follow up survey availability via social media using a Children's Mercy Hospital channel (e.g. Facebook, Twitter, Instagram, etc.).
- Participants will receive a reminder contact about the upcoming survey, sent one week ahead of the 12-week survey (at week 11) via the participant's preferred method of contact and/or social media handle using a Children's Mercy Hospital channel.
- Participants will complete the Follow-up Survey at 12 weeks (completion window 10-14 weeks).
- Participants will receive an email and/or text inviting them to complete the follow-up survey using a weblink provided. We will send up to 2 emails and/or 2 text reminders, as needed. If by week 13 the participant has not completed the follow-up survey, a study team member will call them using the phone number(s) provided to remind them about the survey (maximum number of phone calls = 3). If needed at the time of the call, the follow-up survey weblink will be sent via email and/or text.
- To aid in completion of the Follow-Up Surveys, the study team will check the medical record to see if participants have scheduled appointments at Children's Mercy during the 6 week and 12 week follow-up window. If they have an appointment, or are admitted to Children's Mercy, the study team will approach them at this time to offer opportunity to complete the Follow-up Survey via tablet computer at this appointment.

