26.0 Adverse Events and Unanticipated Problems*

Monitoring: The PI and study team will meet weekly during enrollment and the 3-month follow-up period to identify and discuss adverse events and unanticipated problems. Study team members will promptly notify the PI if an adverse event or unanticipated problem is identified.

Reporting: We will follow Policy 5.11 Reportable Events of the CM Research Program Policies and Procedures in regards to reporting adverse events and other unanticipated problems to the CM IRB.

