28.0 Data and Specimen Management*

Data Management: Data will include that obtained from the study surveys and medical record, as described above.

Data will be collected via REDCap or paper survey or EHR review. Data from the surveys and EHR will be stored in REDCap. Paper surveys, if used in the event of a REDCap or other IT issue, will be stored in a locked office of the investigators.

Deidentified data will be exported from REDCap to statistical programs for analysis (e.g., SAS, SPSS, Excel). All data will be securely stored on password-protected CM servers.

Strict measures will be taken to ensure participant privacy and confidentiality. Participants will be assigned a unique study identification number. Additionally, survey data will be collected using a unique, participant-created code such that a link between participant survey number and participant identity do not need to be linked.³⁹ The study REDCap project will be set up such that the study team will not be able to link survey data to individual participant identity. All personally identifiable information needed to facilitate data collection and intervention fidelity review will be kept strictly confidential, stored on

REDCap, and accessible only to designated study team members. Only study team members needing access to data to fulfill their study responsibilities will have access to the data. Non-study team members will not have access to the data.

Data will be stored per CM records retention policy.

Specimen Management: N/A

Biosafety Information

Will this study involve handling, transporting, or shipping any potentially hazardous biological material at/from a Children's Mercy location (e.g., blood, stool, saliva, tissue)?

Yes

No

Will this study involve processing any potentially hazardous biological material at a Children's Mercy location (e.g., blood, stool, saliva, tissue)?

Yes

No

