## 6 Study Methods

### 6.1 General Study Design and Plan

The ED-HEART pilot has been designed as a randomized controlled trial comparing enhanced standard of care (control study arm) to the ED-HEART intervention. Individuals will be randomized in a 1:1 allocation.

Subjects will be identified from the ED tracking board and approached to see if they would like to participate in the study. Once pre-screening has occurred and consent/assent has been obtained, individuals will fill out a baseline survey. Those in the ED-HEART study arm will additionally be given the ED-HEART intervention and an exit survey. Each arm will receive a 6-week check in and a 12-week follow-up survey. All completed surveys will be completed confidentially and will not contain identifying information. We will use a unique, participant-created code to link study surveys over time. Those individuals that refused to be part of the study will be given the option to complete a refusal survey.

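### Adverse events are recorded only if staff come across them, and no listed question asks about harm from taking part, so few or no events could not be read as no harm

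*SAP*

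**What the plan says.** **Finding events.** SAP 8.6 states that the "PI and study team will meet weekly during enrollment and the 3-month follow-up period to identify and discuss adverse events and unanticipated problems". Protocol 26.0 adds: "Study team members will promptly notify the PI if an adverse event or unanticipated problem is identified". Reporting to the IRB follows an institutional policy whose text is not in the documents.

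**Expectation and reporting.** SAP 8.6: "No adverse events, serious adverse events, and/or death are anticipated", followed by "Provided any adverse events occur, a safety table will be included in the supplement". SAP 10 lists the safety table as a supplement, if applicable. Neither place gives an event definition, a time window, a denominator or a layout by arm.

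**What participants are asked.** Protocol 9.0 lists the survey domains. The Follow-up Survey, in both arms, covers ARA victimization and perpetration, recognition of abuse, self-efficacy, consequences of ARA, and resource knowledge and use. The Exit Survey, in the ED-HEART arm only, covers fidelity, acceptability, self-efficacy, point-of-care resources and ARA disclosure. On the 6-week contact, Protocol 11.0 says: "Participants will complete a 6-week check-in to confirm and update contact information"; Protocol 20.3 adds a question on having turned 18.

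**Contact by arm.** SAP 6.1: "Those in the ED-HEART study arm will additionally be given the ED-HEART intervention and an exit survey". The same section gives both arms the 6-week check-in and the 12-week survey.

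**Traceability.** Under Protocol 28.0 "the study team will not be able to link survey data to individual participant identity".

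**Named risks.** Protocol 14.0 lists breach of confidentiality, mandatory reporting and emotional distress, and judges the distress risk to be minimal.

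**The concern.** The weekly meeting can discuss only what reaches it. The plan names a risk of taking part, distress triggered by the topic, but describes no question that would bring it to light. A participant who was upset afterwards, or whose partner or parent reacted badly to the materials, would be counted only if they volunteered it or staff happened to see it. (The partner or parent route is my inference; the protocol does not name it.)

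The table is then printed only if something surfaces, so a reader of the report could not tell nothing happened from nobody was asked. This is a feasibility pilot whose conclusions on acceptability and promise would naturally inform a larger trial, and a statement that no adverse events occurred would carry weight there that the method does not earn.

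The second issue is the ED visit. One arm has a conversation about relationships and abuse with a health educator, an audio recording and an Exit Survey. The available text describes no matching observation for controls.

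**Working it through.** **1. Routes by which participation-related harm could be recorded**

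| Stage | ED-HEART | Control | Asks about harm from taking part? |
|---|---|---|---|
| ED visit: enrolment and Baseline Survey | yes | yes | not listed |
| ED visit: health educator session, audio recording, Exit Survey (Protocol 9.0, 25.0; SAP 6.1) | yes | not described | not listed |
| 6-week check-in, reminders, up to 3 calls to non-responders (Protocol 11.0) | yes | yes | no: contact details and turning 18 |
| Week-11 reminder; week-12 reminders, up to 3 calls, approach at appointments (Protocol 11.0) | yes | yes | no: survey completion |
| 12-week Follow-up Survey (Protocol 9.0) | yes | yes | ARA and its consequences, not harm from taking part |

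No row asks about participation-related harm. The arms differ only in the second row. The survey's ARA answers are not designated as adverse-event data and the team cannot trace them to a person, so they cannot become cases for the weekly meeting.

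**2. The plan's own figure**

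The documents contain no adverse-event rate, count or precision target. The related figure is the sample size (Protocol 27.0, SAP 7). Exact two-sided Fisher power for 0.55 against 0.30 with 69 per arm is 0.80398, which agrees with the stated 80.4%. Inflation for loss is 69 / (1 − 0.20) = 86.25, rounded up to 87 per arm, 174 in total, as stated. Nothing in this point alters these figures.

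**3. What a blank table could hide (illustration; risk and capture are assumed)**

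Expected recorded events = 174 × risk × capture. Probability of none = (1 − risk × capture)^174.

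| Assumed true risk | Expected, full capture | Expected, 10% capture | P(no events), 10% capture |
|---|---|---|---|
| 2% | 3.5 | 0.35 | 71% |
| 5% | 8.7 | 0.87 | 42% |
| 10% | 17.4 | 1.7 | 17% |

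At 50% capture and 5% risk the chance of a blank table is 1.2%. The answer therefore turns on a capture rate that the plan does not determine.

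**4. Possible imbalance between arms (illustration)**

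Assume equal true risk, ED capture of 80% in ED-HEART and 40% in control, and 10% capture after discharge in both. With a share s of events occurring in the ED, the ratio of recorded events is [0.8s + 0.1(1 − s)] / [0.4s + 0.1(1 − s)].

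- s = 0: 0.10 / 0.10 = 1.0
- s = 0.1: 0.17 / 0.13 = 1.3
- s = 0.5: 0.45 / 0.25 = 1.8
- s = 1: 0.80 / 0.40 = 2.0

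There is no imbalance if every event occurs after discharge. Any excess depends on s and on the assumed ED capture rates.

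**5. What asking would buy**

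The one-sided 95% upper bound after zero reports among n people asked is 1 − 0.05^(1/n). For n = 69 (planned completers in one arm) it is 4.2%. For n = 138 (both arms) it is 2.1%. For all 87 randomised to an arm it would be 3.4%, but only if capture were complete. With unsolicited capture no bound follows, because the number effectively asked is unknown.

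**The case against.** The strongest objection is that this is a brief educational session classed as minimal risk (Protocol 16.0). Social work and advocate support are available around the clock, and every participant gets a resource list (Protocol 14.0). On that view, passive reporting under an institutional policy is proportionate, unlinked surveys are a deliberate protection, and a conditional safety table is a matter of style. The proportionality argument stands: it is why this is an inexpensive improvement and not an error in a stated figure. It does not make an unasked question informative.

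A reader might be tempted to go further in four ways that the documents do not support.

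- **That nothing asks about harm after the ED visit.** The 12-week survey asks both arms about ARA victimization, perpetration and consequences of ARA. Abuse by a partner is a highly relevant harm here.
- **That the trial can say nothing about harm.** ARA victimization at follow-up is compared by arm (SAP 8.1), so an excess under ED-HEART could show, if imprecisely. What is missing is harm attributed to taking part.
- **That the safety data are biased between arms over three months.** Planned contact after discharge is symmetric and includes study-initiated calls and in-person approaches. Unequal observation is confined to the ED visit, and the documents do not say that the table compares arms.
- **That the table will be nearly empty.** This is a prediction that needs event and capture rates the documents do not give.

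There are also limits on what can be seen. Protocol 9.0 lists domains and not items, so a distress item within acceptability cannot be excluded; that domain is in the Exit Survey, for one arm only. The reportable-events policy and the full description of enhanced usual care are not in the available text, so an event definition or control-arm staff contact might be stated there.

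**Conclusion.** The point holds as a gap in ascertainment. Adverse events are found only through unsolicited staff observation, and no listed domain or described contact asks about distress or other harm from taking part. In-ED events may be recorded unequally because the extra observation described is in one arm. No or few recorded events therefore could not be read as absence of participation-related harm.

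The number of events missed and the size of any in-ED imbalance cannot be derived from the documents. The illustrations (a blank table 17% to 71% of the time at 10% capture; a recorded ratio of 1.0 to 2.0) rest wholly on assumed inputs. The conclusion also assumes that the unseen survey items and the institutional policy contain no participant-facing harm question. This is a change worth making because it is cheap; no stated figure is wrong.

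**What to change.** - **Follow-up Survey, both arms.** Add two or three fixed items: distress from participation; an adverse reaction by someone else to participation or to the materials; any other harm the participant attributes to the study.
- **SAP 8.6 and SAP 10.** Replace the conditional sentence with an unconditional one: these items are always reported by arm, with the number asked as denominator and zeros shown. State the event definition and the time window.
- **Other events.** List staff-observed and spontaneously reported events separately by source, because that route is unequal during the ED visit.
- **If follow-up is already complete.** The change log in SAP 9 has an entry dated 6/19/2024, so enrolment may be well advanced. In that case, state in the report that adverse events were not solicited and draw no between-arm safety conclusion.

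**Cost.** A slightly longer survey, an IRB amendment and a few SAP sentences; the sample size does not change. The answers will be anonymous counts that cannot be followed up individually, and any bound from them applies only to those who answer. If 20% are lost as planned, the survey says nothing about them.
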